5.2 Identity and Description of the Comparator

The Kano 2 (Model Number: CP1150) is an OTE sound processor functionally based on the NEO-XS processing chip, which is used in the current commercially available BTE sound processor, Nucleus 7. Kano 2 is smaller than Cochlear's first OTE sound processor, Kano (CP950) and delivers additional connectivity and noise reduction functionalities.

[figure not shown]

Figure 2. External views of the Kano 2 (CP1150) Sound Processor

5.3 Accessory Device Requirements

5.3.1 Cochlear Home Charger

The Cochlear Home Charger is the primary charging device that will store, dry and charge a Kano 2 and/or Kano 3 Sound Processor.

5.3.2 Portable Charger

The Portable Charger can be used to charge the Kano 2 and Kano 3 Sound Processor on the go or when it is inconvenient for the subject to use a Home Charger. The Portable Charger also powers the sound processor as it is charging and contains an internal battery that requires charging before use. The Portable Charger battery takes approximately 3 hours to fully charge.

5.3.3 CR310 Remote Control

The CR310 Remote Control operates on a 2.4 GHz band and can be used to perform basic control functionality such as changing programs, adjusting loudness and selecting active audio sources.

5.3.4 Cochlear Wireless Accessories

Cochlear Wireless Accessories (Table 1) operates on a 2.4 GHz frequency band to deliver wireless audio streaming to Kanso 3 via the NXP2 Protocol. These optional accessories are designed to provide a consistent input level and an improved SNR ratio to overcome the effects of distance and competing noise in specific listening situations (classrooms, telephone conversations, TV viewing).

Table 1: Compatible Cochlear Wireless Accessories

Configuration	Compatible Wireless Accessory
Mini Microphone	Cochlear™ Wireless Mini Microphone, Cochlear™ Wireless Mini Microphone 2, Cochlear™ Wireless Mini Microphone 2+
TV Streamer	Cochlear™ Wireless TV Streamer
Phone Clip	Cochlear™ Wireless Phone Clip

Kanso 3 is also compatible with GN Resound TV Streamer and the GN Resound Mini Microphone, which are based on the Bluetooth 5.2 protocol.

5.3.5 iOS and Android Devices and the Nucleus Smart App

Kanso 3 connects to compatible iOS devices (running iOS 12 or later) that support the Made for iPhone/iPod/iPad (MFi) Hearing Aid functionality via Bluetooth Low Energy. This enables basic control functions (program change, volume adjustment and audio source selection) and direct audio streaming from the iOS device (phone call, media audio and Live Listen). Kanso 3 connects to compatible Android devices (running Android 10 or later) that support Audio Streaming for Hearing Aid (ASHA) functionality, via Bluetooth Low Energy. Compatibility with Android devices enables direct audio streaming capability from the Android device (phone call and media audio).

Kanso 3 is also able to connect to the Nucleus Smart App on Apple devices running iOS 10 or later or Android devices running Android 5 or later to access a full suite of control and monitoring functions.

5.3.6 Retention Accessories

For large skin flap thicknesses or for vigorous activity, retention aids may be necessary to ensure that, if the sound processor becomes detached from the implant magnet, it does not fall on the ground and be at risk of being damaged.

The following retention accessories are compatible with Kanso 3 Sound Processors:

- Headband
- Safety Line
- Kanso Halo Accessory

5.3.7 Aqua+

The Kanso 3 Sound Processor is compatible with a re-usable, sealable Aqua+ accessory that provides ingress protection up to IP68 during use in or around water (e.g. when swimming, surfing, showering etc.).

5.3.8 Cochlear SoftWear Pad

For a recipient who requires a high magnet strength, or who has a thin skin flap, the pressure imposed on their skin by the sound processor may lead to discomfort. The Cochlear SoftWear pad can be applied to the bottom of the sound processor to distribute the pressure imposed on the skin by the magnetic force over a wider area.

5.3.9 Chargers

The Home Charger is the primary charging unit for Kanso 3 Sound Processor and is the same as the charger currently available for Kanso 2. It integrates wireless charging capability with the ability to dry the Kanso 3 Sound Processor.

The Portable Charger is a portable, wearable charging option for the Kanso 2 and Kanso 3 Sound Processor, allowing recipients to have extended on-air time in situations where they require more charge than the integrated sound processor battery can provide.

5.3.10 Programming Adaptor Cable

The CP1150 Programming Adaptor Cable enables the Kanso 3 Sound Processor to be programmed, via connection to either a PIF4 or PIF5.2. When used with a PIF4 and a CP1000 Programming Cable, the Kanso 3 Sound Processor is powered by the PC. When used with a PIF5.2, the Kanso 3 Sound Processor is powered by the CP1000 Rechargeable Battery.

6 OBJECTIVES

6.1 Primary Objective

- To compare adult cochlear implant speech perception in spatially separated speech and noise (SONrearhalf) between the CP1170 sound processor programs, SCAN 2 FF (Automated ForwardFocus ON) and SCAN 2 (ForwardFocus OFF).

6.2 Secondary Objectives

1. To compare adult cochlear implant speech perception in spatially separated speech and noise (SON3) between the CP1170 sound processor programs, SCAN 2 FF (Automated ForwardFocus ON) and SCAN 2 (ForwardFocus OFF).
2. To evaluate adult cochlear implant speech perception in quiet with the CP1170 sound processor and the CP1150 sound processor (commercial version).
3. To compare subjective acceptance and satisfaction between the CP1170 sound processor and the subject's own processor.
4. To compare adult cochlear implant subjective hearing performance between the CP1170 sound processor and the subject's own processor.

6.3 Exploratory Objectives

1. To explore the feasibility of using an Ecological Momentary Assessment (EMA) application in an interventional study to obtain real-time responses from Cochlear implant users.
2. To compare adult cochlear implant speech perception in spatially separated speech and noise (AuSTIN, 65 dB SPL SONrearhalf 4TB) between CP1170 microphone directionalities, SCAN 2 FF Zoom (Automated ForwardFocus ON) and SCAN 2 FF Beam (Automated ForwardFocus ON).
3. To compare adult cochlear implant speech perception in spatially separated speech and noise (AuSTIN, 65 dB SPL SON3 Babble) between CP1170 microphone directionalities, SCAN 2 FF Zoom (Automated ForwardFocus ON) and SCAN 2 FF Beam (Automated ForwardFocus ON).
4. To compare subjective acceptance and satisfaction between microphone directionalities: CP1170 sound processor using SCAN 2 FF Zoom and CP1170 sound processor using SCAN 2 FF Beam.

7 DESIGN OF THE CLINICAL INVESTIGATION

7.1 General

This is a pre-market, prospective, single-site, open-label, within-subject, interventional study of acceptance and performance of the Kanso 3 Sound Processor (Model: CP1170) through actual-use with adult cochlear implant recipients. The IMD is the Kanso 3 Sound Processor, used in conjunction with the investigational version of Custom Sound Pro fitting software, investigational version of Nucleus Smart App. The comparators include acute use of the Kanso 2 Sound Processor (Model: CP1150) to compare performance in quiet and subject's own sound processor (i.e. any BTE or OTE which they entered the study with) to compare subjective performance and acceptance.

The subjects include adults aged 18 years and older who are currently using a Cochlear hearing implant. Subjects will be screened and 20 eligible subjects will be recruited in the clinical investigation from a single investigational site located in Australia. After enrolment, subjects will attend scheduled study visits for a period up to 12 months as described in the CIP Schedule of Events (Section 3). At study visits, subjects will undergo hearing assessments. Safety will be assessed by recording and summarising all Adverse Events (AE)/ Adverse Device Effects (ADE) and Device Deficiencies (DD). No data monitoring committee will be used for this clinical investigation. All subjects will attend an end-of-study visit at the time they complete the study.

The primary endpoint is to determine the hearing performance of the Kanso 3 Sound Processor with the new implementation of ForwardFocus in SCAN 2 (SCAN 2 FF), as assessed by speech perception in noise. Safety will be assessed by recording and summarising all AEs/ADEs and DDs. No data monitoring committee will be used for this clinical investigation. All subjects will attend an End-of-Study visit at the time they complete the study.

7.1.1 Design Rationale

Experienced adult cochlear implant recipients have been chosen as the study population due to their ability to compare sound processors across generations, in and outside of controlled test environments. In addition, performance benefits achieved by adults can generally be extrapolated to younger age groups, avoiding the need to recruit this vulnerable population.

Comparison will be made within-subject with repeated measures for each of the sound processing conditions to be evaluated. There will be at least 5 in-clinic visits with take home use between each visit. The test sessions will include speech perception tests including sentence in noise and words in quiet tests and may include the completion of questionnaires and usability assessment. These speech measures are routine outcome measures used to evaluate new signal processing algorithms and hardware.

There will be no blinding of the study investigators.

Blinding of the study subject will be undertaken where possible, particularly when multiple signal processing conditions are loaded onto a single study device. Participants will not be told which program will be used in which order, and due to the similar form factor of the sound processor generations, it may also be possible to conceal which sound processor is being used during testing.

Counter-balancing of the test order will be undertaken where possible to limit the influence of order effects on results.

Each take-home period will be a minimum of 2 weeks, allowing a period sufficient to represent a realistic test of the performance of the device and allow any risks associated with ADEs over that period to be identified and assessed. As per the adaptive procedure outlined in Section 6.3.3, should DDs occur resulting in the subject being unable to complete a minimum 2-week take home period, actual-use testing may be paused until the subject can return to the clinic to have the issue investigated and rectified.

7.2 Subjects

Written, informed consent must be obtained from the subject before any study procedures are initiated.

To maintain confidentiality, subject names will not be recorded on any study document other than the informed consent form and Subject ID Log; neither document will be provided to the Sponsor. All individuals who provide informed consent are considered enrolled into the study and will be assigned a unique identifier. If a subject signs consent and either exits the study or fails the screening assessments prior to initiating Visit 1, they will be considered a screen failure and will not be counted as part of the required 20 subjects for the study.

The subjects include adults aged 18 years or older with at least 3 months experience with a Cochlear sound processor. Subjects will be screened, and 20 eligible subjects will be recruited in the clinical investigation. For speech perception testing, all subjects will receive all treatment and control conditions; however, the test order will be counterbalanced/ randomised to control for order effects.

7.2.1 Inclusion Criteria

Subjects must meet all of the inclusion criteria described below to be eligible for this clinical investigation.

1. Aged 18 years or older
2. Post linguually deafened[‡]

[‡] Pre-lingually deafened subjects with adequate speech comprehension (as evidenced by compliance with inclusion criterion 6) are considered acceptable for enrolment.

3. Implanted with the CI600 Series (CI612, CI632, CI622, CI624), CI500 Series (CI512, CI532, CI522), Freedom Series (CI24RE(CA), CI24RE(ST), CI422), N24 Series (CIC3).[§]
4. At least 6 months experience with a cochlear hearing implant.
5. At least 3 months experience with any Nucleus sound processor and SCAN program.
6. Able to score 30% or more at +15 SNR with CI alone on a sentence in babble test
7. Willingness to participate in and to comply with all requirements of the protocol
8. Fluent speaker in English as determined by the investigator
9. Willing and able to provide written informed consent

7.2.2 Exclusion Criteria

Subjects who meet any of the exclusion criteria described below will not be eligible for this clinical investigation.

1. Additional disabilities that would prevent participation in evaluations
2. Unrealistic expectations on the part of the subject, regarding the possible benefits, risks and limitations that are inherent to the procedures
3. Unable or unwilling to comply with the requirements of the clinical investigation as determined by the Investigator
4. Investigator site personnel directly affiliated with this study and/or their immediate families; immediate family is defined as a spouse, parent, child, or sibling
5. Cochlear employees or employees of Contract Research Organisations or contractors engaged by Cochlear for the purposes of this investigation, as determined by the Investigator.
6. Current participation, or participation in another interventional clinical study/trial in the past 30 days, involving an investigational drug or device (unless the other investigation was/is a Cochlear sponsored investigation and determined by the investigator or Sponsor to not impact this investigation).

7.2.3 Number of Subjects Required

A total of twenty subjects are to be recruited to meet the sample size calculation requirements (Section 9.4) with a dropout rate of no more than 15%.

7.2.4 Vulnerable Populations

Pregnant women will not be excluded from this study. The study procedures including the investigational devices will have no impact on the health and safety of this population.

7.2.5 Recruitment and Study Duration

The following subject status definitions apply:

- Enrolled: A subject that has signed the Informed Consent form for the study.

[§] All implant models considered acceptable for enrolment are listed in Section 5.1.1.3.1: Indications.

- Screen Fail: An Enrolled subject that has been determined to not meet one or more eligibility criteria.
- Participated: Subjects who have met eligibility criteria and have commenced baseline assessments.
- Discontinued: An Enrolled subject who withdrew consent, was discontinued by the Investigator or Sponsor before the expected End of Study visit, or lost to follow-up. Discontinued subjects may still have safety follow up data collection until their scheduled End of Study visit, for reasons described in section 7.2.6.
- Completed: Enrolled subjects who complete the required treatment and visit schedule.

The recruitment period for the clinical investigation is estimated to be up to 3 months from the time of first subject consent to recruitment of the last subject.

The expected duration of each subject's participation in the clinical investigation, is up to 12 months from the time of informed consent through to the End of Study visit.

Clinical Investigation completion is last subject last visit. In the event of an ongoing Serious Adverse Events (SAEs) or Serious Adverse Device Effects (SADEs) at the time of this last visit, the clinical investigation completion will be extended for a further 30 days, or until resolution or stabilisation of the event, whichever comes first.

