To compare adult cochlear implant speech perception in spatially separated speech and noise (AuSTIN, 65 dB SPL SON3 Babble) between CP1170 microphone directionalities, SCAN 2 FF Zoom (Automated ForwardFocus ON) and SCAN 2 FF Beam (Automated ForwardFocus ON).	Paired difference in dB SRT (AuSTIN, 65 dB SPL SON3 Babble) between the CP1170 SCAN 2 FF Zoom (Automated ForwardFocus ON) and CP1170 SCAN 2 FF Beam (Automated ForwardFocus ON).
To compare subjective acceptance and satisfaction between microphone directionalities: CP1170 sound processor using SCAN 2 FF Zoom and CP1170 sound processor using SCAN 2 FF Beam.	Ratings based on the CP1170 Questionnaire after a minimum 2-weeks actual-use of the CP1170 sound processor SCAN 2 FF Zoom and CP1170 sound processor SCAN 2 FF Beam.

3 Schedule of Events

Visit Type	Screening	Visit 1 ^a	Visit 2 ^b	Ad Hoc ^c	EOS ^d
Timing of Investigation	Day 0	Day 0	Week 2	NA	Month 12
Visit window (±)	NA	+ 7 days	+ 14 days	NA	± 30 days
Written informed consent	X				
Demographics	X				
Eligibility	X				
Hearing history	X				
Device history	X				
Medical history	X				
Baseline Questionnaire ^e		X			
SSQ12 - Own Processor ^f		X			
SSQ12 - CP1170 Sound Processor ^g				X	
APHAB Questionnaire				X	
CP1170 Fitting ^h		X		X	
Fitting optimisation ⁱ			X	X	
Speech perception testing - Speech in Noise ^{jk}				X	
Speech perception testing – Words in Quiet ^l				X	

^a Screening and visit 1 may occur on the same day.

^b Visit 2 signifies the end of the first take-home period. Procedures from Ad Hoc visits may be performed on the same day as required.

^c Ad Hoc refers to any unscheduled visit and may be repeated.

^d EOS can occur on the same day as an Ad Hoc visit.

^e Information regarding the subject's own sound processor, i.e. that which they had been using prior to screening, and usage habits.

^f Own processor is defined as the sound processor that the subject used for a minimum of 2 weeks prior to their enrolment.

^g SSQ12 on the IMD following the final take-home period.

^h First fitting of the investigational sound processor.

ⁱ Fitting optimisation is subject to need and may include programming changes, and hardware or firmware modifications or updates to the investigational sound processor.

^j In-booth testing CP1170 SCAN 2 ForwardFocus ON compared with the CP1170 ForwardFocus OFF (65 dB SPL S0Nrearhalf 4-talker babble).

^k CP1170 ForwardFocus ON (SCAN 2) and ForwardFocus OFF (SCAN 2) (65 dB SPL S0N3 babble).

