7.2.6 Criteria and Procedures for Subject Withdrawal

Subjects can decide to withdraw from the investigation at any time. The Investigator shall ask the reason(s), however subjects have the right to withhold their reason if preferred. The reason for withdrawal should be documented in the subject's source files and the electronic case report form (eCRF), if provided.

The Investigator or Sponsor may also decide to withdraw a subject from the clinical investigation or stop the use of the investigational device if it is considered to be in the subject's best interests.

Subject withdrawal may be for any of the following reasons:

- Adverse Event (AE)
- Device Deficiency (DD)
- CIP or GCP deviation
- Subject withdrew consent
- Subject lost to follow-up
- Subject death
- Sponsor decision
- Investigator decision
- Other (specify)

If a subject is lost to follow-up, every possible effort must be made by the study site personnel to contact the subject and determine the reason for discontinuation. At least 3 separate attempts taken to contact the subject must be documented.

Participating subjects who are withdrawn/discontinued will not be replaced.

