7.3.1.4 End of Study Visit

- Collection of final SSQ12 Questionnaire following CP1170 use: *see Section 7.3.2.6.1*.
- Collection of any remaining questionnaires (e.g. EMA or CP1170 Questionnaire) provided as part of final take-home period (as required).
- Return devices and study completion: At the end of the study, subjects will return all IMDs and associated components and revert to full-time use of their own device with the commercially available firmware.

The EOS visit can occur on the same day as an Ad Hoc visit.

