7.3.2.6 Subjective Ratings

7.3.2.6.1 Speech, Spatial and Qualities of Hearing Scale (SSQ12)

The SSQ is designed to measure a range of hearing disabilities across several domains. Subjects are asked to rate their ability to hear speech in a variety of competing contexts, subjects are also asked about their spatial hearing abilities including the impact of direction, distance and movement associated with spatial hearing. Subjects are also asked about their ease of listening, and the naturalness, clarity and identifiability of different speakers (Gatehouse & Noble, 2004; Noble, Jensen, Naylor, Bhullar, & Akeroyd, 2013). A shortened form of the 49-question SSQ, the SSQ12, will be used in this study.

Study subjects will be asked to complete the SSQ12 at two time points in the study; 1) at study entry, where scores will reflect their experience with their own sound processor, 2) after take home use with the Kanso 3 Sound Processor.

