8.3 Risks Associated with Participation in the Clinical Investigation

There is a risk that the programs on the investigational sound processor may sound different to the subject's own sound processor. Other risks may include exacerbation of existing tinnitus and a reduction in the sound quality or intelligibility of the research programs. Subjects are advised to return to their own processor and promptly inform the investigators if these events occur. Possible interactions with concomitant medications and residual risks for the device are not anticipated in this clinical investigation.

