9.5 Analysis Populations

This study has a non-inferiority design; therefore, the primary endpoint analysis will be based on the Per Protocol population (PP).

For cases in which the Intent-to-Treat (ITT) and PP populations lead to the same conclusions and interpretations about the treatment effect, the results will be considered to not be influenced by underlying factors such as missing data and protocol deviations, and the results would be considered to be robust and consistent under different analysis populations. A statement to reflect this will be included in the Clinical Investigation Report.

For cases in which the ITT and PP populations lead to different final conclusions or interpretations, the results will be reported for both analysis sets and the differences in outcomes will be identified and explored.

Intent-to-Treat Population

The ITT Population will include all subjects who consented and participated (refer Section 7.2.5).

For the purposes of the analyses of the primary and secondary endpoints, subjects will be included in the analysis regardless of protocol deviations. Missing data will not be imputed. Consequently, only subjects with paired treatment and control measurements will contribute to the analysis.

Per Protocol Population

The PP will include all subjects who have one set of paired measurements from treatment and control (for speech outcomes or SSQ12), without major protocol deviations. Major deviations will be defined at the clean file meeting before database lock. Treatment administration not conducted in the intended counterbalanced order of presentation will also be regarded as a protocol violation. However, it is expected that the sequence and period effects are minimal in this study, if any.

This analysis set will be the primary analysis set for the testing of non-inferiority (primary and secondary hypotheses).

Safety Population

The Safety Population will include all treated subjects. The Safety Population will be used for the safety data analysis.

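### SSQ12 endpoint: no CP1170 form is required from subjects who stop early, so both PP and ITT omit them and PP/ITT agreement says nothing about missing SSQ12 data

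*Combined protocol and SAP*

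**What the plan says.** **Collection.** Section 7.3.2.6.1: "Study subjects will be asked to complete the SSQ12 at two time points in the study". One is at entry for the own processor, the other after home use of the CP1170. Section 3, footnote g, times the second as "SSQ12 on the IMD following the final take-home period", and Section 7.3.1.4 lists under the End of Study visit "Collection of final SSQ12 Questionnaire following CP1170 use". Participation can last up to 12 months.

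**Leaving early.** Section 7.2.6 lists adverse events and device deficiencies among the withdrawal reasons and adds: "Participating subjects who are withdrawn/discontinued will not be replaced". For data after discontinuation, Section 7.2.5 offers only this: "Discontinued subjects may still have safety follow up data collection until their scheduled End of Study visit, for reasons described in section 7.2.6". Neither section mentions an SSQ12 at that point.

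**Foreseen reasons to stop.** Section 8.3 names poorer sound quality or intelligibility and worsened tinnitus as risks. It continues: "Subjects are advised to return to their own processor and promptly inform the investigators if these events occur".

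**Analysis.** Non-inferiority on SSQ12 is concluded if the lower limit of the two-sided 95% CI for the mean paired difference lies above -1 (9.6.2), tested in PP. PP requires a treatment/control pair. In ITT, too, "only subjects with paired treatment and control measurements will contribute to the analysis". Missing data are not imputed (9.1, 9.5). Section 9.5 then treats agreement between ITT and PP as showing that missing data and deviations did not influence the result.

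**The concern.** SSQ12 asks how well the subject hears with the CP1170 relative to the own processor. A subject who leaves because the CP1170 sounds worse leaves for a reason that overlaps the outcome. If this happens before the single CP1170 form, the subject has a baseline score and no partner score.

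Two consequences follow. First, the remaining subjects are on average more favourable to the CP1170, so the observed mean difference moves upward, away from the -1 margin, and false non-inferiority becomes more likely. Second, the safeguard in 9.5 cannot detect this. The two sets differ in how they treat protocol deviations but omit the same unpaired subjects, so they can agree however informative the loss is.

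**Working it through.** **Step 1. The plan's own sample size.** Inputs from 9.4: margin 1 dB, SD of the paired difference 1.36 dB, one-sided alpha 0.025, power 0.80. The true difference is taken as 0. For a paired t test the power is P(T > t(0.975, n-1)), where T is noncentral t with n-1 df and noncentrality 1 × √n / 1.36.

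- n = 16: power 0.785
- n = 17: noncentrality √17/1.36 = 3.03, power 0.812

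So 17 evaluable subjects are needed, and 17/0.85 = 20. Both stated figures reproduce. The attrition allowance is 20 × 0.15 = 3 subjects. It covers all causes and was set for the primary endpoint.

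**Step 2. Who can be missing.** Section 7.1.1 plans at least 5 clinic visits with home use between them, each period at least 2 weeks. Read literally, that is at least 4 × 2 = 8 weeks of CP1170 use before the only CP1170 SSQ12. A subject who leaves within that time has no required form and drops out of PP and ITT.

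**Step 3. Effect on the SSQ12 test.** The documents give no SSQ12 SD and no expected dropout for poor sound, so these are assumptions:

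- 20 paired differences, normal, true mean exactly -1, SD 1.0, 1.5 or 2.0.
- k subjects lost, being those with the lowest value of ρ × (standardised difference) + √(1-ρ²) × (independent noise). ρ = 0 means loss unrelated to the rating, ρ = 0.5 a moderate link, and ρ = 1 the k worst raters.
- Non-inferiority declared if mean - t(0.975, 19-k) × s/√(20-k) > -1.

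Probability of falsely declaring non-inferiority (200,000 simulated trials per setting):

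| Lost | Unrelated | ρ = 0.5 | Worst raters |
|---|---|---|---|
| 0 | 0.025 | 0.025 | 0.025 |
| 1 | 0.025 | 0.041 | 0.075 |
| 2 | 0.025 | 0.061 | 0.156 |
| 3 | 0.025 | 0.081 | 0.258 |

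With the true mean at the margin the t statistic is free of scale, so these rates do not depend on the SD. The upward shift in the observed mean does. With 3 lost:

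| SD | ρ = 0.5 | Worst raters |
|---|---|---|
| 1.0 | 0.13 | 0.26 |
| 1.5 | 0.20 | 0.39 |
| 2.0 | 0.26 | 0.52 |

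These shifts are to be read against a margin of 1.

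**The case against.** **Going back to the own processor is not leaving the study.** Section 8.4 has subjects revert until the cause is understood and resolved. Sections 7.1.1 and 7.3.2.5 allow a take-home period to be paused, and the adaptive procedure in 7.3.2.7 turns sound-quality complaints into product updates and re-evaluation. Section 7.2.6 also separates stopping use of the device from withdrawing the subject. This stands, and it lowers the likely number of losses. A reader might infer that every subject who reverts is lost; the text does not say so. A subject who stopped home use but stayed in the study could still complete the form at End of Study, with the last period used counted as the final one. But nothing requires that reading of footnote g, and nothing covers a subject who leaves.

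**Safety-only follow-up is inferred from silence.** Correct. Section 7.2.5 permits safety collection and does not forbid other data. The gap is the missing requirement. Where consent is withdrawn or contact is lost, no later form can be obtained in any case.

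**Early dissatisfaction is visible elsewhere.** The CP1170 Questionnaire is given after the first take-home period (7.3.2.6.3), withdrawal reasons are summarised (9.1), and discontinuations for adverse events are reported (9.7). This helps interpretation but supplies no value to the SSQ12 test.

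**The larger error rate is extreme.** It is. It requires the whole all-cause allowance to be used by the three worst raters, with the true mean at the margin. The 0.5 correlation is likewise assumed. No figure in the documents points to any dropout for poor sound.

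**The other non-inferiority endpoints.** A reader might extend the bias to the SRT and CNC endpoints. The documents do not support this. Those are booth comparisons at Ad Hoc visits with no fixed window (7.3.1.3), with both conditions of an endpoint tested on one day (7.3.4). A pair is lost only if the subject leaves before testing. The two SRT comparisons set programs on the same CP1170 against each other, and nothing links disliking the device to that difference. No bias is shown for CNC either.

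**Conclusion.** The point holds for the SSQ12 secondary endpoint only. The single late form, the absence of any requirement at stopping, and the paired-only rule in both sets mean that an early leaver is absent from PP and ITT together. This follows from the text and needs no assumption. It also makes the 9.5 inference about missing data invalid for SSQ12.

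The size is conditional. At the planned 15% attrition and a true mean at -1, a moderate link between loss and rating roughly triples the nominal 2.5% error. About 26% is a bound for three losses, not an expectation. Unrelated loss leaves the error at 2.5%, and no such dropouts means no bias. This is a cheap improvement to a secondary endpoint and does not put the primary conclusion in doubt.

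**What to change.** 1. **Collection (Section 3 footnote g; 7.2.5, 7.2.6, 7.3.2.6.1).** Require the CP1170 SSQ12 on the day device use is permanently stopped, or at early termination, from subjects who still consent. Where still possible, also give it with the CP1170 Questionnaire after the first take-home period.
2. **Endpoint rule (9.2.2, 9.5).** Use the score after the final take-home period where it exists, otherwise the last observed CP1170 SSQ12. Apply this in both PP and ITT and state that early stopping alone is not a major deviation. Used in ITT only, it would leave the formal PP test unchanged.
3. **Interpretation (9.5).** State that PP/ITT agreement is not evidence about missing SSQ12 data.
4. **Reporting (9.1, 9.6.2).** Give the number of missing CP1170 SSQ12 forms with reasons, and add a sensitivity analysis assigning unfavourable values to those still missing. This needs a stated exception to the no-imputation rule.

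Cost: a 12-item form at contacts that mostly take place already, plus wording. Early scores reflect shorter use and possibly earlier firmware. Section 25 records that all subjects had been recruited by version 3, so the form after the first take-home period may come too late for some. The stopping-day form remains possible for anyone still participating, and the analysis rules can be set until the SAP is final before database lock (14.3).
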